	
 
Reduction of HESD score, HESD itch score, and HESD pain score, (weekly averages) of ≥4 points from parent baseline at each nominal week from baseline up to Week 36.
 

	Health-related quality of life
	
 
HEIS score at each scheduled visit with assessment from baseline up to Week 36.
 

	
 
HEIS (each individual domain) score at each scheduled visit with assessment from baseline up to Week 36.
 

	
 
DLQI score at each scheduled visit with assessment from baseline up to Week 36.
 

	
 
EQ-5D-5L visual analogue score at each scheduled visit with assessment from baseline up to Week 36.
 

	
 
EQ-5D-5L index score at each scheduled visit with assessment from baseline up to Week 36.
 

	
 
WPAI:CHE domain scores at each scheduled visit with assessment from baseline up to Week 36.
 

	Exposure and treatment compliance
	
 
Total amount of delgocitinib cream 20 mg/g used during the trial.
 

	Percentage of missed applications.

- 1. In the derivation of HECSI-75 and HECSI-90 the baseline score from the parent trials will be used.
- 2. An on-treatment period is defined from the day treatment is re-initiated (when IGA-CHE score ≥2 is observed by the investigator) to the day treatment is stopped (when IGA-CHE score of 0 [clear] or 1 [almost clear] is observed by the investigator).
- 3. Number of response days (days when a subject is not on treatment with delgocitinib cream 20 mg/g) divided by number of days between baseline and end of trial.

Page 33 of 121

4. Response days are defined as the sum of days where the subject is in response periods. A response period is defined as the period from the day IGA-CHE score of 0 (clear) or 1 (almost clear) is observed by the investigator, to the day IGA-CHE score ≥2 is observed by the investigator.

5. Among subjects with a parent baseline HESD score, HESD itch score, and HESD pain score (weekly averages) ≥4 points, respectively

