#### Follow-up period (Week 36 to Week 38)

All subjects will complete a 2-week off-treatment follow-up period for the assessment of safety. The safety follow-up period will start after the Week 36 visit (end-of-treatment). Note that for subjects who permanently discontinue delgocitinib cream 20 mg/g, the 2-week follow-up period will start at the time of the early termination visit.

The safety follow-up visit will be performed via phone, but can be a site visit if needed.

Serious AEs (SAEs) will be followed up until a final outcome is established as described in Section 13.7.

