## 7.3 End-of-trial definition

A subject is considered to have completed the trial if they completed the treatment period and the safety follow-up visit at Week 38.

For an individual subject, end of trial is defined as attending the last visit (or phone visit) in the trial.

The end of the trial overall is defined as the date of the last visit of the last subject in the trial globally.

Page 38 of 121

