# 10.3 Early termination assessments

#### Permanent discontinuation of IMP

Subjects who permanently discontinue IMP prior to Week 36 will be asked to attend the following visits:

- Early termination visit (as soon as possible).
- Safety follow-up visit (phone visit approximately 2 weeks after attending the early termination visit).

See the schedule of trial procedures (Section 4) for assessments to be done at these visits. The investigator will review any AEs which will be followed up according to Section 13.7, if the subject agrees.

Page 52 of 121

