## 14.3.6 Analysis of other/exploratory endpoints

All analyses are based on safety analysis set.

The number of on-treatment days from baseline up to Week 36 will be summarised.

The number of on-treatment periods from baseline up to Week 36 and the rates per 100 person years of observation time will be presented.

The proportion of response days (days with IGA-CHE 0 or 1) from baseline up to Week 36 will be summarised. Mean duration of on-treatment periods per subject from baseline up to Week 36 will be summarised.

Time to first IGA-CHE score ≥2, initiation of rescue treatment, or discontinuation of IMP, whichever occurs first, will be presented for the subjects in the safety analysis set who were previously treated with delgocitinib cream 20 mg/g twice daily in the parent trial and achieved IGA-CHE TS at Week 16 in the parent trial. Kaplan-Meier curve and estimates will be presented. Subjects will be censored at the date of the last assessment visit in case of no events. Follow-up time to first IGA-CHE score ≥2 starts from the baseline visit.

Time to first response (IGA-CHE 0 or 1) will be presented for the subjects in the safety analysis set who did not achieve IGA-CHE TS at Week 16 in the parent trial, by treatment group assigned in the parent trial (delgocitinib cream 20 mg/g or cream vehicle respectively). Kaplan-Meier curves and estimates will be presented. Subjects will be censored at the date of the last assessment visit, initiation of rescue treatment, or discontinuation of IMP, whichever occurs first. Follow-up time to first response will be derived from the baseline visit.

Time to response (IGA-CHE 0 or 1) following treatment re-initiation after first off-treatment period will be presented for subjects in the safety analysis set who were treated with delgocitinib cream 20 mg/g twice daily in the parent trial. Kaplan-Meier curves and estimates will be presented. Subjects will be censored at the date of the last assessment visit, initiation of rescue treatment, or discontinuation of IMP, whichever occurs first. Follow-up time to response will be derived from the visit of treatment re-initiation after first off-treatment period.

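### Proportion of response days: the footnote 3 parenthesis equates response with being off cream, contradicting footnote 4 and Section 14.3.6 (exploratory endpoint, minor)

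*Combined protocol and SAP*

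**What the plan says.** Three statements bear on the numerator of this endpoint.

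- Section 6, Panel 3, footnote 3: "Number of response days (days when a subject is not on treatment with delgocitinib cream 20 mg/g", which is then "divided by number of days between baseline and end of trial".
- Section 6, Panel 3, footnote 4: "Response days are defined as the sum of days where the subject is in response periods". Such a period opens only when the investigator observes IGA-CHE 0/1, and it closes when a score ≥2 is observed.
- Section 14.3.6: "The proportion of response days (days with IGA-CHE 0 or 1) from baseline up to Week 36 will be summarised".

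Footnote 3 is attached to the word for proportion and footnote 4 to the word for response, on the same endpoint line.

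Other sections fix the days in question. Section 10.2 lists lack of efficacy, adverse events and rescue among the reasons for permanent discontinuation and bars a restart. Section 7.1 calls the two weeks after the Week 36 visit off treatment and adds: "for subjects who permanently discontinue delgocitinib cream 20 mg/g, the 2-week follow-up period will start at the time of the early termination visit". Section 10.3 asks subjects who discontinue to attend an early termination visit and then a "Safety follow-up visit (phone visit approximately 2 weeks after attending the early termination visit"). Section 7.3 states: "For an individual subject, end of trial is defined as attending the last visit (or phone visit) in the trial".

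**The concern.** While every start and stop of cream follows an observed IGA-CHE score, being off cream and being at 0/1 are the same thing, and the three statements agree. They separate when cream stops for a reason other than response. A subject who stops for lack of efficacy with IGA-CHE ≥2 is off cream for the rest of their time in the trial. Footnote 3 makes those days response days; footnote 4 and Section 14.3.6 do not. The same split affects a completer still on cream at Week 36, who is off treatment until Week 38.

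No other rule settles the matter. The non-responder imputation in Sections 14.3.5, 14.3.7 and 14.3.13 covers binary responses, not a proportion of days. Panel 2 schedules no IGA-CHE at the safety follow-up, so no observed score would correct the credit.

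The endpoint describes disease control under as-needed use. Two programmers could each follow the protocol and obtain different values, and one of them would be counting some treatment failure as response.

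**Working it through.** The plan states no numerical result for this endpoint, so there is no figure to reproduce. The check is a day count.

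**Inputs**

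- Schedule (Panel 2): Week 36 is Day 1 + 36×7 = 253 and Week 38 is Day 1 + 38×7 = 267, so a completer has 267 − 1 = 266 days from baseline to end of trial.
- Follow-up after the early termination visit: about 2 weeks, taken as 14 days (Sections 7.1, 9.5 and 10.3).
- Delay *d* from last application to the early termination visit: the protocol says only as soon as possible. Assumed range: 0 to 14 days.
- End of trial: the subject's own last visit or phone visit (Section 7.3).

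**Test case.** A subject has IGA-CHE ≥2 at baseline, uses cream from Day 1, never reaches 0/1, stops permanently at Week *w*, and attends both the early termination visit and the follow-up.

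- Literal footnote 3: (*d* + 14) / (7*w* + *d* + 14)
- Footnote 4 and Section 14.3.6: 0, because no response period ever opens

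| Stop | Footnote 3, *d* = 0 | Footnote 3, *d* = 14 | Footnote 4 and 14.3.6 |
|---|---|---|---|
| Week 4 | 14/42 = 33.3% | 28/56 = 50.0% | 0% |
| Week 8 | 14/70 = 20.0% | 28/84 = 33.3% | 0% |
| Week 16 | 14/126 = 11.1% | 28/140 = 20.0% | 0% |
| Week 24 | 14/182 = 7.7% | 28/196 = 14.3% | 0% |
| Completer, on cream to Week 36 | 14/266 = 5.3% | not applicable | 0% |

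The credited days are the same in every row of a column. Only the denominator changes, so the proportion is larger for an earlier stop.

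**Window.** The endpoint and Section 14.3.6 run to Week 36, while the footnote 3 denominator runs to end of trial. If the numerator were cut at Week 36, the completer's 14 days would drop out. The Week 4 to Week 24 rows would not change, because those follow-ups end before Week 36.

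**Ordering of subjects.** Take a completer with 56 days at 0/1 who relapses and is on cream at Week 36. Literal footnote 3 gives (56 + 14)/266 = 26.3%, below the 33.3% of the never-responder who stops at Week 4. Counting only the days at 0/1 gives 56/266 = 21.1% against 0%.

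**Cohort mean.** The plan gives no number of such subjects. If an assumed share *f* stops at Week 16 without response and with no delay, the mean rises by *f* × 14/126. For *f* = 5% this is 0.6 percentage points, and for *f* = 20% it is 2.2.

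**The case against.** The strongest reply is that the sound definition is already in the plan. Footnote 4 is attached to the response term and is worded as a definition, Section 14.3.6 agrees with it, and the parenthesis in footnote 3 is only a gloss inside a ratio. This stands in part. The defect is one clause against two concordant statements, and the credit appears in the results only if footnote 3 is programmed. But no precedence is stated, and footnote 3 is where the ratio is specified.

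A second reply is that footnote 2 ends an on-treatment period when 0/1 is observed, and Section 14.3.8.1 derives on/off status for adverse events from IGA-CHE. On that reading a never-responder stays on treatment throughout and gains nothing. The text does not force this reading, and Section 7.1 points the other way by calling the follow-up weeks off treatment, including for those who discontinue.

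Three limits on the point are right:

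- Not every subject who stops has IGA-CHE ≥2. An adverse event or pregnancy can end treatment at 0/1, and footnote 4 then also counts response days.
- The credit can be nil. Under Section 10.3, subjects who withdraw from the trial are asked only for an early termination visit, and some may attend no further visit.
- The endpoint is exploratory and only summarised, and Section 14.1 rules out comparative analyses.

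**Conclusion.** Wrong as written, and minor. The numerator is defined inconsistently, and the literal footnote 3 rule counts off-cream days at IGA-CHE ≥2 as response. For a never-responder this is about 14 days plus any delay to the early termination visit. With no delay, that is 33% down to 8% for stops from Week 4 to Week 24 and 5.3% for a completer, against 0% under footnote 4 and Section 14.3.6. The figures assume that the follow-up takes place 14 days after the early termination visit; the completer figure also assumes a numerator that runs to end of trial. The effect on the cohort mean is small, about 0.6 to 2.2 percentage points under the assumed 5% to 20% stopping at Week 16. Primary and secondary results are unaffected.

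A reader might infer two stronger conclusions that the documents do not support:

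- That the plan as a whole credits treatment failures with response. It does so in one of three statements; the other two give no such credit.
- That earlier failures gain more response days. That would need a fixed Week 38 end for everyone (for a Week 4 stop, 238/266 = 89.5%). Section 7.3 ends the trial at each subject's own last visit, so the days are roughly constant and only the proportion grows.

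**What to change.** Delete the parenthesis in footnote 3. State in Section 6 and Section 14.3.6 that the only numerator is the number of days from an observed IGA-CHE 0/1 to the next observed score ≥2, with response periods truncated at the end of the endpoint's analysis window. The truncation is needed because footnote 4 gives no closing event for a subject who leaves while at 0/1. State that window explicitly, since the endpoint runs to Week 36 and the footnote 3 denominator to end of trial.

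The cost is one footnote and one derivation, and a reported proportion slightly less favourable than under literal footnote 3.

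Removing response days after discontinuation in subjects who stop while at IGA-CHE 0/1 would be a separate choice. It would discard response that was actually observed, and it is not part of this correction.

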### 6 Trial objectives and endpoints

Panel 3: Objectives and endpoints

Objectives	Endpoints
Primary objective	Primary endpoint
To evaluate the long-term safety of an as-needed treatment with twice-daily applications of delgocitinib cream 20 mg/g.	Number of treatment-emergent AEs from baseline up to Week 38.
Secondary objective	Secondary endpoints
To evaluate the long-term efficacy of an as-needed treatment with twice-daily applications of delgocitinib cream 20 mg/g.	
 
IGA-CHE score at each scheduled visit from baseline up to Week 36.
 
IGA-CHE score of 0 (clear) or 1 (almost clear) at each scheduled visit from baseline up to Week 36.
 
HECSI score at each scheduled visit from baseline up to Week 36.
 
HECSI-75 at each scheduled visit from baseline up to Week 36.
 
HECSI-90 at each scheduled visit from baseline up to Week 36.
 

Other/exploratory objectives	Other/exploratory endpoints
To explore efficacy, health-related quality of life, and work productivity for an as-needed treatment with twice-daily applications of delgocitinib cream 20 mg/g.	
 
Efficacy
 
Number of days on treatment with delgocitinib cream 20 mg/g from baseline up to Week 36.
 
Number of on-treatment periods² from baseline up to Week 36.
 

Page 32 of 121

Objectives	Endpoints
	
 
Proportion of response days from baseline up to Week 36.
 

	
 
Mean duration of on-treatment periods per subject from baseline up to Week 36.
 

	
 
Time to first IGA-CHE score ≥2 in subjects previously treated with delgocitinib cream 20 mg/g in the parent trial and who achieved IGA-CHE TS at Week 16 in the parent trial.
 

	
 
Time to first response (IGA-CHE score of 0 [clear] or 1 [almost clear]) in subjects who did not achieve IGA-CHE TS at Week 16 in the parent trial.
 

	• Time to response (IGA-CHE score of 0 [clear] or 1 [almost clear]) following treatment re-initiation after first off-treatment period in subjects previously treated with delgocitinib cream 20 mg/g in the parent trial.
	
 
HESD score (weekly average) at each nominal week from baseline up to Week 36.
 

	
 
HESD itch, pain, cracking, redness, dryness, and flaking scores (weekly averages) at each nominal week from baseline up to Week 36.
 

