#### Treatment period (Week 0 up to Week 36)

#### **Definition of terms:**

**Response** is defined as IGA-CHE score of 0 (clear) or 1 (almost clear).

Treatment re-initiation is triggered by an IGA-CHE score of  $\geq 2$  after having achieved IGA-CHE 0 (clear) or 1 (almost clear) in this trial.

At baseline (Day 1), subjects will be evaluated by the investigator to determine the severity of their CHE. Subjects with IGA-CHE score of 0 (clear) or 1 (almost clear) will not be assigned treatment with delgocitinib cream 20 mg/g; they will however continue to use their routine skin care emollient, if applicable. Subjects with IGA-CHE score ≥2 will start treatment with twice-daily delgocitinib cream 20 mg/g. Treatment will continue until IGA-CHE score of 0 (clear) or 1 (almost clear) is achieved.

If a subject experiences worsening of CHE signs and symptoms while off-treatment, the subject should contact the trial site. If a scheduled visit is not planned within a reasonable timeframe, an unscheduled visit should be planned as soon as possible. If an IGA-CHE score  $\geq 2$  is attested, the subject will be dispensed delgocitinib cream 20 mg/g and the investigator will instruct the subject to start treatment with twice-daily applications. The minimal set of assessments to be performed at an unscheduled visit to decide if treatment with delgocitinib cream 20 mg/g should be re-initiated is IGA-CHE and collection of AEs.

While on treatment with delgocitinib cream 20 mg/g, if the subject observes that CHE signs and symptoms are resolved, they should contact the trial site. If a scheduled visit is not planned within a reasonable timeframe, an unscheduled visit should be planned as soon as

Page 36 of 121

possible. If IGA-CHE score of 0 (clear) or 1 (almost clear) is achieved, the subject will be instructed to stop treatment and return all opened and unopened tubes to the site. The minimal set of assessments to be performed at an unscheduled visit to decide if treatment with delgocitinib cream 20 mg/g should be stopped is IGA-CHE, collection of AEs, and investigator's assessment of local tolerability.

For all subjects, regardless if on- or off-treatment, IGA-CHE will be evaluated by the investigator at visits to the trial site every 4 weeks from baseline up to Week 36.

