#### 10.2 Reasons for discontinuation of IMP

Subjects will permanently discontinue IMP in the event of:

- An AE that, in the judgement of the investigator or sponsor's medical expert, contraindicates further dosing.
- Evidence of pregnancy.
- Initiation of rescue treatment.
- Lack of efficacy.
- Clinically important laboratory abnormalities:
  - Alanine aminotransferase (ALT) and/or aspartate aminotransferase (AST) values >3× upper limit of normal (ULN) with total bilirubin >2×ULN (unless elevated bilirubin is related to Gilbert Meulengracht Syndrome) and at the discretion of the investigator.
  - o Confirmed ALT and/or AST values >5×ULN (for more than 2 weeks).
- Positive reaction to IMP patch test.

It is not allowed to restart IMP treatment after permanent discontinuation of IMP.

Page 51 of 121

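### The proportion of response days covers baseline to Week 36 but is divided by days to end of trial (Week 38 for completers), a shift of 0 to 5.3 points whose direction the text leaves open

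*Combined protocol and SAP*

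**What the plan says.** Panel 3 (Section 6) lists the endpoint as "Proportion 3 of response 4 days from baseline up to Week 36", where the 3 and the 4 are footnote marks. Section 14.3.6 keeps the same window: "The proportion of response days (days with IGA-CHE 0 or 1) from baseline up to Week 36 will be summarised". It gives no denominator.

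Footnote 3 to Panel 3 supplies the only one. It takes the number of response days, explains them in a parenthesis, and divides: "days when a subject is not on treatment with delgocitinib cream 20 mg/g) divided by number of days between baseline and end of trial". Footnote 4 defines the same days differently: "Response days are defined as the sum of days where the subject is in response periods". A response period there opens when the investigator observes IGA-CHE 0 or 1 and closes when IGA-CHE of 2 or more is observed.

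End of trial is a defined term in Section 7.3: "For an individual subject, end of trial is defined as attending the last visit (or phone visit) in the trial". The same section requires the Week 38 follow-up visit for completion. On the last two weeks, Section 7.1 says: "All subjects will complete a 2-week off-treatment follow-up period for the assessment of safety".

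**The concern.** The endpoint is about the time to Week 36, yet the number it is divided by runs to the follow-up contact. A proportion is interpretable only if its count and its base cover the same days. Here they do not, and no other section reconciles them.

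The numerator is also open. The title and Section 14.3.6 stop it at Week 36. Footnote 3 itself carries no such cut, and it describes response days as days off the cream. Every subject is off the cream during follow-up, and the schedule in Section 4 has no IGA-CHE there. Two programmers could both claim to follow the protocol and produce different values for every completer.

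At stake is the accuracy of one descriptive summary of disease control under as-needed use. The primary and secondary endpoints do not use this quantity.

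**Working it through.** The documents give no figure for this endpoint, so there is none to reproduce. The check is day arithmetic on the visit schedule.

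**Inputs**
- Section 4, Panel 2: baseline is Day 1, the Week 36 visit Day 253, and follow-up Day 267, each post-baseline visit with a window of ±3 days.
- Days to Week 36: 253 − 1 = 252. Days to end of trial for a completer: 267 − 1 = 266. Difference: 14.
- R is the number of response days up to Week 36, from 0 to 252.

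**Formulas for a completer at nominal days**
- Matched window: R/252.
- Reading A, numerator cut at Week 36 and denominator to end of trial: R/266. Shift from matched = −(R/252)(14/266).
- Reading B, days off treatment counted to end of trial: (R+14)/266. Shift from matched = (14/266)(1 − R/252).
- 252/266 = 0.947 and 14/266 = 0.053.

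| R | R/252 | A: R/266 | Shift (points) | B: (R+14)/266 | Shift (points) |
|---|---|---|---|---|---|
| 0 | 0% | 0% | 0 | 5.3% | +5.3 |
| 63 | 25% | 23.7% | −1.3 | 28.9% | +3.9 |
| 126 | 50% | 47.4% | −2.6 | 52.6% | +2.6 |
| 189 | 75% | 71.1% | −3.9 | 76.3% | +1.3 |
| 252 | 100% | 94.7% | −5.3 | 100% | 0 |

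Readings A and B differ by 14/266 = 5.3 points for every completer.

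**A mixed case.** Footnote 4 closes a response period only at an observed IGA-CHE of 2 or more, and none is scheduled after Week 36. If open periods run on to end of trial, completers with IGA-CHE 0 or 1 at Week 36 follow B and the others follow A.

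**Sensitivity of the 0.947.** Counting both end days gives 253/267 = 0.948. With the ±3-day windows, the factor under A runs from 249/269 = 0.926 to 255/263 = 0.970.

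**Early leavers.** Subjects who permanently discontinue IMP, including for rescue, are asked to attend an early termination visit and a follow-up about two weeks later (Sections 9.5 and 10.3). With the numerator cut at early termination:
- Week 16: 112/(112 + 14) = 112/126 = 0.889.
- Week 24: 168/182 = 0.923.

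That cut is an assumption, because the title's Week 36 limit does not impose it. Section 10.3 asks subjects who withdraw only for the early termination visit. If that is their last contact, there is no tail and the factor is 1.

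**The case against.** Three arguments count against making much of this.

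First, the sign is not settled. A reader might infer that footnote 3 simply understates response, and that a subject clear throughout can never reach 100%. The documents do not support that as a general statement. It follows only when the Week 36 cut from the title is combined with the denominator from footnote 3. Taken on its own wording, footnote 3 admits the 14 follow-up days, and the error then runs upward. This objection stands, and the conclusion below is conditional for that reason.

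Second, a reader might take footnotes 3 and 4 as two plainly conflicting definitions of response. Footnote 2 weakens that inference, because it defines an on-treatment period by the IGA-CHE scores that start and stop it. On that reading, being off treatment is largely the complement of the same state, and for subjects managed as planned the two agree up to Week 36. What remains is narrower. If footnote 3 is read as actual use of the cream, days after permanent discontinuation would count as response even when IGA-CHE is 2 or more, since "It is not allowed to restart IMP treatment after permanent discontinuation of IMP". Remote start or stop decisions under the COVID-19 plan are taken without an IGA-CHE and could move the count either way. The documents give no frequency for either case, so no cohort effect can be stated.

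Third, the endpoint is exploratory and no comparative analysis is planned. That is correct, and it limits the importance of the point. It does not remove the mismatch.

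**Conclusion.** The point holds. The endpoint's window ends at Week 36, and its only stated denominator ends at Week 38 for a completer. At nominal visit days the distortion is 0 to 5.3 points per completer. It is an understatement (factor 0.947) if the numerator stops at Week 36, and an overstatement, largest for subjects who never respond, if days off treatment are counted to end of trial. The title and Section 14.3.6 favour the first reading, but the text does not exclude the second.

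The effect is not confined to completers, and 5.3 points does not bound the whole cohort. Subjects who discontinue permanently and attend follow-up carry a proportionally larger tail, while subjects who withdraw may carry none. The distortion therefore varies with disposition and is not one common rescaling. Its cohort average cannot be computed, because the documents give neither discontinuation rates nor the distribution of R.

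The impact is minor: one exploratory, descriptive endpoint.

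**What to change.** In Panel 3 footnote 3:
- Replace 'end of trial' with 'the Week 36 (end-of-treatment) visit or the early termination visit, whichever is earlier'.
- State that the numerator ends at the same visit.
- Replace the parenthesis about not being on treatment with footnote 4's IGA-CHE-based definition of a response day, as in Section 14.3.6.

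Repeat the denominator in Section 14.3.6, so that the analysis text is complete on its own.

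The anchor should be a visit, not the date treatment ended. Treatment stops repeatedly in this as-needed design, and the end-of-treatment form in Section 11.9 records the date of last application. A subject who stops at Week 8 and stays clear would lose exactly the response days the endpoint is meant to measure. A subject already clear or almost clear at baseline is not assigned treatment and might have no such date.

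The cost is footnote wording and programming. No new data are needed, and trial conduct does not change.
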